3.4.2. Other Anticancer Therapy

For purposes of this protocol, anti-tumor treatment may be defined as, but is not limited to, anti-cancer agents (anti-estrogen endocrine therapy, cytotoxic chemotherapy, immunotherapy, or biologic therapy), radiotherapy, and investigational agents. An investigational agent is any drug or therapy not currently approved for use in humans. No other anticancer therapy is permitted during the course of the study treatment for any patient (the patient can receive a stable dose of corticosteroids during the study as long as these were started at least 4 weeks prior to enrollment and the total daily dose does not exceed 10mg of prednisone, or the equivalent, per exclusion criteria above). If the patient discontinues study treatment, this restriction no longer applies; however, the patient will remain enrolled in the study for the purpose of collecting subsequent outcomes.

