5.6. Recommended Dose Modifications

Every effort should be made to administer each investigational product at the planned dose and schedule.

In the event of significant toxicity, dosing may be interrupted, delayed and/or reduced, only as described for each investigational product. In the event of multiple toxicities, treatment/dose modifications should be based on the worst toxicity observed. Patients are to be instructed to notify Investigators at the first occurrence of any adverse symptom.

Treatment/dose modifications may occur independently for each investigational product in the combination based on the observed toxicity and the general guidance, as follows:

- a. SM-88: Dose modifications (dose interruptions, or dose reductions) may be implemented to manage toxicities.
 - i. If SM-88 is held then MPS should be held concurrently.
- b. Methoxsalen, phenytoin, and sirolimus (MPS): No dose reductions are permitted in this study, but if methoxsalen, phenytoin, or sirolimus are considered to be the component associated with a grade 3 or 4 toxicity, the individual components may be discontinued for up to 28 days while mitigating measures are attempted (e.g. changing the timing of phenytoin to address phenytoin related fatigue if experienced). This may be applied to any or all of the MPS components. If after 28 days the grade > 2 toxicity continues, the patient will be removed from the study. If the patient restarts the MPS medication(s) but the toxicity recurs then the 28 day hold clock restarts so that further mitigation efforts can be implemented; if multiple holds are required then it is at investigator discretion if the patient should continue or come off the study.
 - i. If any or all components of MPS are held then SM-88 can be continued at investigator discretion.

The RP2D of SM-88 is 920 mg/day administered as two 230 mg capsules every 12 hours. For patients experiencing a grade 3 or 4 toxicity, dose modifications of SM-88 can be made as outlined in **Table 4 and Table 5**.

Table 4. Dose Modifications for Toxicities Related to SM-88

Dose Level	SM-88 Dose	Dose Adjustment for Next Treatment
1	460 mg BID (920 mg/day)	Decrease dose to 230 mg BID
-1	230 mg BID (460 mg/day)	Discontinue study treatment for up to 28 days and attempt mitigation; if this dose is not tolerated then patient should be removed from the study

Table 5. Management of Toxicities Related to SM-88 and MPS

	SM-88 + MPS
Hematologic Toxicities	

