Grade 1 and 2	No requirement for dose interruption or dose reduction
Anemia Grade \geq 3 (hemoglobin < 8 g/dL or transfusion indicated)	
1st occurrence: Hold SM-88 and MPS; monitor at least weekly and if hemoglobin recovers to ≥ 8 g/dL within 28 days then resume drugs and decrease SM-88 to dose level -1. Transfusion of blood and blood products are permitted.Recurrence: Hold SM-88 and MPS; monitor at least weekly and if hemoglobin recovers to ≥ 8 g/dL within 28 days resume drugs and patient can remain on study at investigator discretion.Permanently discontinue SM-88 and MPS if these parameters have not been met after 28 days of dose interruption.
Neutropenia Grade \geq 3 (ANC $< 1000/\text{mm}^3$) associated with a documented infection or fever $\geq 38.5^\circ\text{C}$	
1st occurrence: Hold SM-88 and MPS; monitor at least weekly and if ANC recovers ($\text{ANC} \geq 1000/\text{mm}^3$) within 28 days, then resume drugs and decrease SM-88 to dose level-1. Hematopoietic growth factors are not permitted.Recurrence: Hold SM-88 and MPS; monitor at least weekly and if ANC recovers ($\text{ANC} \geq 1000/\text{mm}^3$) within 28 days then resume drugs at same dose level.Permanently discontinue SM-88 and MPS if these parameters have not been met after 28 days of dose interruption.
Grade 4 neutropenia (ANC $< 500/\text{mm}^3$)	
1st occurrence: Hold SM-88 and MPS. Monitor at least weekly and if ANC recovers to $\geq 1000/\text{mm}^3$ in ≤ 7 days, then resume study drugs at same dose level. If ANC remains $< 1000/\text{mm}^3$ for > 7 days, hold SM-88 and MPS until ANC $\geq 1000/\text{mm}^3$ and decrease SM-88 to dose level -1.Recurrence: Hold SM-88 and MPS; monitor at least weekly and if ANC recovers ($\text{ANC} \geq 1000/\text{mm}^3$) within 28 days then decrease SM-88 to dose level -1 or resume drugs at same dose level if already at dose level -1.Permanently discontinue SM-88 and MPS if these parameters have not been met after 28 days of dose interruption.

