Thrombocytopenia Grade \geq 3 (platelets $< 50,000/\text{mL}$)	
Hold SM-88 and MPS; monitor at least weekly and if platelets recover ($\geq 50,000/\text{mL}$) within 28 days, then resume drugs at same dose level.If Grade 3 thrombocytopenia (platelets $< 50,000/\text{mL}$) with bleeding, hold SM-88 and MPS. Monitor at least weekly and if platelets recover ($\geq 50,000/\text{mL}$) and bleeding stops within 28 days, resume drugs and decrease SM-88 to dose level -1.If Grade 4 thrombocytopenia (platelets $< 25,000/\text{mL}$), hold SM-88 and MPS. Monitor at least weekly and if platelets recover ($\geq 50,000/\text{mL}$) within 28 days, resume drugs and decrease SM-88 to dose level -1.Permanently discontinue SM-88 and MPS if Grade ≥ 3 thrombocytopenia (platelets $< 50,000/\text{mL}$) recurs or persists for > 28 days.
Non-hematologic Toxicities	
Grade 1 and 2	
No requirement for dose interruption or dose reduction.
Grade ≥ 3	
1st occurrence: Hold SM-88 and MPS; monitor and if toxicity decreases to Grade 1 or to baseline within 28 days, then resume drugs and decrease by SM-88 to dose level -1.

	
 • Recurrence: Hold SM-88 and MPS; monitor and if toxicity decreases to Grade 1 or to baseline within 28 days then resume drugs at same dose level. • Exceptions are: Nausea, vomiting, or diarrhea lasting ≤72 hours; fatigue lasting ≤ 7 days; hypertension controlled with medical therapy; increase in indirect bilirubin indicative of Gilbert's syndrome; serum lipase or amylase lasting ≤ 7 days without clinical signs or symptoms of pancreatitis; endocrinopathies controlled with hormonal therapy; laboratory values that do not have any clinical correlate.
--	---

All dose modifications should be clearly documented in the patient's medical chart and in the CRF.

6. Safety Variables and toxicity assessment

The Principal Investigator or Sub-Investigators will assess adverse events, laboratory data, and vital signs throughout the study. Adverse events will be assessed by NCI CTCAE Version 5.0.

https://ctep.cancer.gov/protocoldevelopment/electronic_applications/docs/CTCAE_v5_Quick_Reference_5x7.pdf

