6.8. General Management of Significant Toxicities

6.8.1. Significant Toxicities Management

The following are general guidelines for dose delay and discontinuation of the study drugs if a patient experiences an adverse event; Refer to **Table 5** for specific guidance:

- Patients may delay treatment for up to 28 days to allow the toxicity to resolve. If the toxicity requiring dose interruption has not resolved completely or to CTCAE Grade 1 (or to baseline if Grade 2 at time of study entry) during the maximum 28-day dose interruption period, the patient must permanently discontinue treatment on study
- Patients may restart therapy if toxicity(ies) resolve to Grade 1 or lower (or to baseline if Grade 2 at time of study entry).
- If a dose interruption is required at any point on study because of hematologic toxicity, weekly blood draws for CBC will be monitored until the AE resolves or the patient comes off study.
- The patient must be referred to a hematologist for further evaluation (1) if frequent (at investigator discretion) transfusions are required or (2) if the treatment-related hematologic toxicities have not recovered to CTCAE Grade 1 or less after 28 days.
- For major surgery while on treatment, up to 28 days of study treatment interruption is allowed.
- All dose interruptions (including any missed doses), and the reasons for the reductions/interruptions, are to be recorded.

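### On residual Grade 2 toxicity after a 28-day hold of a conditioning agent, Section 5.6(b) is out of line with 6.8.1 and Table 5; Table 5 and 5.6(b)(i) also disagree on whether SM-88 is held

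*Combined protocol and SAP*

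**What the plan says.** All references are to the combined protocol and SAP.

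**Section 5.6(b)** covers the three conditioning agents. Doses cannot be reduced, but a component blamed for a Grade 3 or 4 toxicity may be stopped for up to 28 days. Then: "If after 28 days the grade > 2 toxicity continues, the patient will be removed from the study". The next sentence deals with patients who restart MPS and have the toxicity again, but 5.6(b) names no grade at which restart is allowed. Sub-item i adds: "If any or all components of MPS are held then SM-88 can be continued at investigator discretion".

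**Section 6.8.1** gives general guidance for all study drugs and sends the reader to Table 5 for specifics. If the toxicity has not cleared, or fallen to Grade 1 (or to a Grade 2 baseline), "during the maximum 28-day dose interruption period, the patient must permanently discontinue treatment on study". Restart has the same threshold.

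**Table 5, non-hematologic, Grade 3 or above**, first occurrence: "Hold SM-88 and MPS; monitor and if toxicity decreases to Grade 1 or to baseline within 28 days, then resume drugs", with SM-88 reduced to dose level -1. The recurrence line uses the same threshold. Neither line says what happens if it is not met. The anemia and neutropenia rows do: "Permanently discontinue SM-88 and MPS if these parameters have not been met after 28 days of dose interruption". The thrombocytopenia row has its own permanent-stop line.

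**Section 4.3.12 (note)** lets the other study drugs continue when one MPS agent has to be discontinued, at the investigator's discretion after consulting the sponsor. If SM-88 is stopped, MPS stops too.

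**The concern.** A rule for stopping treatment on safety grounds should give one answer for one patient. Here a site that follows 5.6(b) may keep a patient with residual Grade 2 toxicity on treatment, while a site that follows 6.8.1 must stop. A reader who turns to Table 5, as 6.8.1 directs, finds no day-28 outcome in the relevant row. Enrolment is spread over five centers.

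At stake are consistent safety management and two descriptive items under the secondary safety objective (Section 2.2): dose delays or reductions, and discontinuations for adverse events. The second depends directly on which day-28 rule a site applies, and the first on which hold rule it applies. The hold question arises at the start of any qualifying event, not only when Grade 2 toxicity remains at day 28.

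**Working it through.** **Step 1: the day-28 rules side by side.** The plan gives no figure to reproduce, so this is a comparison of texts. The case is a non-hematologic Grade 3-4 toxicity attributed to an MPS component and outside the Table 5 exceptions.

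| Grade at day 28 | 5.6(b) | 6.8.1 | Table 5, non-hematologic row |
|---|---|---|---|
| 0-1 | No removal | May restart | Resume |
| 2, baseline 2 | No removal | May restart | Resume (at baseline) |
| 2, baseline below 2 | No removal (2 > 2 is false) | Permanent discontinuation | Resume condition not met; no outcome stated |
| 3-4 | Removal | Permanent discontinuation | Resume condition not met; no outcome stated |

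The rules part in one row only: Grade 2 with a baseline below Grade 2. There 6.8.1 and Table 5 share the threshold of Grade 1 or baseline, and 5.6(b) stands alone.

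**Step 2: why hematologic toxicity is left out.** For these events Table 5 sets its own recovery values (hemoglobin 8 g/dL, ANC 1000/mm3, platelets 50,000/mL) and its own permanent-stop lines. As 6.8.1 defers to Table 5 for specifics, those rows can stand.

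**Step 3: the hold itself.** Table 5 says to hold both SM-88 and MPS at Grade 3 or above, with no condition on attribution. Section 5.6(b)(i) allows SM-88 to continue while any MPS component is held. Section 6.3.4.3 makes the investigator attribute every event to a named agent or combination, so both routes can be used in practice.

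SM-88 taken over one full 28-day hold, at the starting dose of 460 mg twice daily:

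- Table 5: 0 mg.
- 5.6(b)(i), SM-88 continued: 460 mg x 2 x 28 = 25,760 mg at most.

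**Step 4: frequency.** This cannot be computed. The documents give neither residual grades at day 28 nor the share of Grade 3-4 events attributed to a conditioning agent.

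**The case against.** The strongest reply is that there is no true contradiction. Section 5.6(b) says when a patient is removed; it never says that a Grade 2 patient may restart. Stopping satisfies all three texts. Its wording could also mean that the original Grade 3-4 event persists at whatever grade. This stands in part: the conflict lies between a removal rule that is not triggered and a mandatory stop, and a cautious site can comply with both. But the literal threshold in 5.6(b) is above Grade 2, and the text goes straight on to restarting MPS, so a site that keeps the patient on is not misreading it.

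A reader might infer that the intended rule cannot be recovered, since Table 5 says "No requirement for dose interruption or dose reduction" for Grade 1 and 2 toxicity and so seems to tolerate Grade 2. The documents do not support that. That row covers toxicity arising at Grade 1 or 2; recovery from Grade 3 or above has its own row, which agrees with 6.8.1. The change log for version 1.5 also says these sections were edited to be consistent. The intended threshold is legible, and 5.6(b) was not brought into line with it.

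On the hold, 5.6 says modifications may be made independently for each product. So 5.6(b)(i) can be read as the rule for a component-attributed toxicity and Table 5 as the rule for the combination. That is reasonable, and the fix adopts it. But Table 5's title covers toxicities related to MPS as well as SM-88, and the row does not make the distinction.

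Finally, a blanket permanent stop would cut across the 4.3.12 note and the instructions in 6.8.3 to stop only phenytoin or only sirolimus for certain reactions. This stands in full and shapes the fix.

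**Conclusion.** The point holds as a minor drafting conflict in a safety rule. For non-hematologic Grade 3-4 toxicity attributed to a conditioning agent, with a baseline below Grade 2 and Grade 2 at day 28, 5.6(b) does not remove the patient, 6.8.1 requires a permanent stop, and Table 5 withholds resumption without giving an outcome. The separate hold conflict is worth 0 mg against up to 25,760 mg of SM-88, assuming a full 28-day hold with every dose taken at the starting level.

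The path is probably rare. The drug-specific stop rules in 6.8.3 and the exceptions in Table 5 take some toxicities out of it. Monthly site calls (3.7.4) and quarterly review by the safety committee (6.2.1) may catch a case but supply no rule. The Grade 3-4 event and the interruption are recorded whichever rule is followed.

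Two further inferences are tempting and are not made:

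- **Dose after the hold.** A reader might set 460 mg/day under Table 5 against 920 mg/day under 5.6(b)(i). But 5.6(b)(i) speaks only of the period while components are held and sets no later dose.
- **The primary test.** A patient who stops for intolerance before first restaging is not evaluable and is replaced (3.6.2.1), so a reader might infer an effect on the response test. Stage sizes and cut-offs do not change, and no document gives a frequency from which an effect could be sized.

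**What to change.** 1. In 5.6(b), for non-hematologic toxicity, replace the day-28 removal sentence with: *If after 28 days the toxicity has not resolved to Grade 1 or baseline, the implicated MPS component is not restarted and study treatment is permanently discontinued, unless the investigator, after consulting the sponsor, continues the other study drugs under 4.3.12; follow-up continues.* Follow-up after stopping fits Section 3.4.2, under which "the patient will remain enrolled in the study for the purpose of collecting subsequent outcomes".
2. Add the same day-28 outcome to the non-hematologic Grade 3 or above row of Table 5.
3. In 6.8.1, cross-refer to the 4.3.12 exception.
4. Keep the Table 5 recovery values for hematologic toxicity.
5. In the same Table 5 row, state that SM-88 and MPS are both held unless the toxicity is attributed only to a conditioning agent, in which case 5.6(b)(i) applies.

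The cost is one sentence in 5.6(b), edits to one table row and one cross-reference. It adds no visits, scans or patients. The downside is that a few patients with residual Grade 2 toxicity will stop a component, or all treatment, who might have continued under the present 5.6(b).

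### For Grade 3-4 toxicity attributed to an MPS component, sections 5.6(b), Table 5 and 6.8.1 give inconsistent rules for stopping and restarting treatment

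*Combined protocol and SAP*

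**What the plan says.** Section 5.6 opens with a general permission: "Treatment/dose modifications may occur independently for each investigational product in the combination based on the observed toxicity". Item (b) then covers Grade 3 or 4 toxicity linked to an MPS component. That component may be held for up to 28 days while mitigation is tried. If toxicity above Grade 2 is still present after that, the rule is "toxicity continues, the patient will be removed from the study". On recurrence, "If the patient restarts the MPS medication(s) but the toxicity recurs then the 28 day hold clock restarts", and whether a patient needing several holds stays on study is left to the investigator. On SM-88 the text reads "If any or all components of MPS are held then SM-88 can be continued at investigator discretion".

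Tables 4 and 5 are introduced by a sentence saying that for Grade 3 or 4 toxicity "dose modifications of SM-88 can be made as outlined in" the tables. Table 5 is nevertheless titled "Management of Toxicities Related to SM-88 and MPS". Each of its five Grade 3-or-higher rows holds SM-88 together with MPS. Its thrombocytopenia row ends in permanent discontinuation of SM-88 and MPS if the event recurs or lasts beyond 28 days. Its non-hematologic row restarts at Grade 1 or baseline and lists exceptions, among them fatigue of at most 7 days.

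Section 6.8.1 describes itself as general guidance for the study drugs and points to Table 5 for specifics. It says a patient must stop permanently if, within the 28-day maximum, the toxicity has not resolved or come down to Grade 1 (or to baseline if Grade 2 at entry).

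**The concern.** These are stopping rules for Grade 3-4 toxicity in a trial with five sites. Two sites could manage the same MPS-attributed event differently, each citing the protocol. One would stop a patient with recurrent severe thrombocytopenia for good; the other would hold and re-challenge. One would discontinue at day 28 for residual Grade 2 toxicity; the other would find no instruction in 5.6(b) to do so.

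Patient safety comes first. In addition, dose delays, dose reductions and discontinuations due to adverse events are a stated secondary objective, so the inconsistency also blurs what those counts mean across sites. The cause of an event can be uncertain as well: 5.6(b) gives as an example "changing the timing of phenytoin to address phenytoin related fatigue if experienced", while section 1.3 describes fatigue as a known effect of the L-isomer contained in SM-88.

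**Working it through.** The plan states no figure on this point, so the check is a comparison of rules followed by a rough count of patients.

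**Case 1: recurrent Grade 3 or higher thrombocytopenia, attributed to an MPS component**
- Table 5: permanent discontinuation of SM-88 and MPS.
- 5.6(b): new 28-day hold; repeat holds at the investigator's discretion.
- Result: 5.6(b) allows a re-challenge that Table 5 forbids. Attribution to MPS is plausible, since 6.8.3.1 lists thrombocytopenia among complications reported with phenytoin.

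**Case 2: status at day 28**
- 5.6(b): removal if above Grade 2; nothing said about Grade 2.
- 6.8.1: permanent stop unless resolved, Grade 1, or baseline if Grade 2 at entry.
- Table 5, non-hematologic: restart at Grade 1 or baseline, in line with 6.8.1. Here 5.6(b) is the odd one out.
- Table 5, hematologic: restart at hemoglobin 8 g/dL, ANC 1000 or platelets 50,000. For anemia the rule is recovery to at least "8 g/dL within 28 days then resume drugs and decrease SM-88 to dose level -1". Each value is the edge of the table's own Grade 3 range, so a patient just reaching it is at Grade 2, not Grade 1. Each is also below the entry minimum (hemoglobin 9 g/dL, ANC 1,500, platelets 100,000), so reaching it need not mean a return to the baseline value. Here the literal wording of 6.8.1 is the odd one out.

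**Case 3 (lesser): SM-88 while MPS is held**
- 5.6(b)(i): SM-88 may continue, up to 28 × 920 mg = 25,760 mg over a full hold.
- Table 5: SM-88 held, 0 mg. Three rows (anemia, neutropenia with infection or fever, non-hematologic) always restart SM-88 at 230 mg BID after the first event. The other two (Grade 4 neutropenia, thrombocytopenia) do so only under conditions.

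**How many patients**

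Section 1.3 reports three at least possibly related Grade 3 events among 38 patients in Part 1 of the pancreatic trial (both SM-88 doses), hence in 1 to 3 patients. Exact (Clopper-Pearson) 95% intervals, scaled to 50 patients:

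| Patients | Rate (95% CI) | Per 50 (95% CI) |
|---|---|---|
| 1/38 | 2.6% (0.07-13.8%) | 1.3 (0.03-6.9) |
| 3/38 | 7.9% (1.7-21.4%) | 3.9 (0.8-10.7) |

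The same section also mentions a patient with related serious arthralgia and hypotension. If that is the Grade 3 arthralgia patient, the count stands. If it is another patient, also from Part 1, the ceiling becomes 4/38 = 10.5%, or 5.3 of 50.

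No related Grade 3 or higher event is reported in 30 first-in-human patients (upper 95% limit 11.6%; different conditioning mix) or in 23 prostate patients (upper limit 14.8%), both at lower SM-88 doses.

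These figures cover any study drug. The MPS-only share is not reported, so I take 0 to 100%: about 0 to 4 of 50 at the point estimate with three patients. Section 1.3 names no thrombocytopenia, so Case 1 is probably rare.

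**Design figures**

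With 30 then 20 patients, continuing at 3 or more responses and rejecting at 8 or more of 50, type I error is 0.0955 at a response rate of 0.095 and power is 0.802 at 0.20. Neither depends on the toxicity rules.

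**The case against.** The strongest reply is that the texts can mostly be read together. Section 5.6 allows modification drug by drug, 5.6(b) applies only when an MPS agent is judged responsible, and the tables are introduced as guidance for changing the SM-88 dose. Section 4.3.12 separately lets the other drugs continue when one MPS agent is stopped, in consultation with the sponsor. On that reading, continuing SM-88 is an express discretion. A reader might infer a flat contradiction on holding SM-88, but the documents do not support that: a site that follows Table 5 breaches nothing in 5.6(b), and Table 5 has printed exceptions and no row for Grade 3 neutropenia without infection or fever. What stands is that Table 5's title includes MPS and nothing says which text governs toxicity due to MPS alone.

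A reader might also infer that 5.6(b) permits restarting at Grade 2. It does not; it is silent, and 6.8.1 can fill the gap. Nor is it fair to say that no precedence exists between 6.8.1 and Table 5, since 6.8.1 defers to the table for specifics. That softens the hematologic mismatch but leaves a mandatory stop in 6.8.1 that the table does not follow.

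On recurrent thrombocytopenia the reply is weaker. Stopping complies with both texts, but re-challenging complies with 5.6(b) and not with Table 5.

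**Conclusion.** The inconsistency is real and should be corrected. The clearest part is recurrent Grade 3 or higher thrombocytopenia. The day-28 threshold comes next, as a mixture of silence in 5.6(b) and mismatch between 6.8.1 and Table 5. The SM-88 hold is an ambiguity only.

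The size is small: a handful of patients at most on the point estimates, possibly none. This assumes that toxicity rates from other tumor types and partly lower doses carry over, and it leaves the MPS-only share open. The day-28 finding takes the Grade >2 limit as printed; if at least Grade 2 was meant, most of the gap between 5.6(b) and 6.8.1 closes, though the text still needs correcting.

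A reader might infer harm to the primary analysis. The design's type I error and power are unchanged; the issue is safety and uniform management.

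**What to change.** Three short edits:

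1. In 5.6(b), state that the permanent-discontinuation rules in Table 5, including the one for recurrent Grade 3 or higher thrombocytopenia, override 5.6(b).
2. Use one day-28 recovery threshold in 5.6(b), Table 5 and 6.8.1 (both its stop and its restart bullets): Grade 1 or baseline for non-hematologic events, and the Table 5 laboratory value for hematologic events.
3. Say in one sentence whether 5.6(b)(i) or the Table 5 hold applies to SM-88 when toxicity is attributed only to an MPS component. Either choice is defensible and is the sponsor's to make.

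The cost is a brief amendment, with no change to sample size, visits or design figures. A few patients with residual Grade 2 non-hematologic MPS toxicity at day 28, or with recurrent thrombocytopenia, would stop treatment, as 6.8.1 and Table 5 already require. A few with hematologic recovery to the Table 5 value but not to Grade 1 could resume, as Table 5 already allows.

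### Table 5 gives two different SM-88 doses for a first episode of ANC < 500/mm³ with infection or fever that recovers within 7 days

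*Combined protocol and SAP*

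**What the plan says.** Table 5 in section 5.6 of the combined protocol and SAP handles neutropenia in two consecutive rows.

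- **Infection/fever row.** The trigger is Grade ≥ 3 neutropenia (ANC < 1000/mm³) "associated with a documented infection or fever" of at least 38.5 °C. At first occurrence, treatment is held. If ANC returns to ≥ 1000/mm³, the instruction is "within 28 days, then resume drugs and decrease SM-88 to dose level-1. Hematopoietic growth factors are not permitted". At recurrence with the same ANC recovery, it is "within 28 days then resume drugs at same dose level".
- **Grade 4 row.** The trigger is ANC < 500/mm³. At first occurrence with ANC back to ≥ 1000/mm³ in at most 7 days, it reads "then resume study drugs at same dose level". If recovery takes longer than 7 days, SM-88 goes to dose level -1. At recurrence with recovery within 28 days, it reads "then decrease SM-88 to dose level -1 or resume drugs at same dose level if already at dose level -1".

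Table 4 sets level 1 at 460 mg BID and level -1 at 230 mg BID. Both neutropenia rows stop treatment permanently if recovery has not occurred after 28 days.

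**The concern.** The first row has no lower ANC bound, and the second is not limited to patients without infection or fever. ANC < 500/mm³ with infection or fever therefore falls under both, and the rows do not always lead to the same dose.

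Section 5.6 is headed as recommendations, but it says that "dosing may be interrupted, delayed and/or reduced, only as described for each investigational product". Two sites could each follow Table 5 and restart the same patient on different doses after a serious event. Dose reductions are also among the safety outcomes in section 2.2, so such an event could be counted as a reduction at one site and not at another.

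**Working it through.** No sample-size or error-rate figure is involved, and the plan states no figure to reproduce. The check applies both rows to one patient with ANC < 500/mm³ and infection or fever, and compares the SM-88 dose on restart.

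| Situation | Infection/fever row | Grade 4 row | Result |
|---|---|---|---|
| First episode on 460 mg BID, recovery in ≤ 7 days | 230 mg BID | 460 mg BID | conflict |
| First episode on 460 mg BID, recovery in > 7 to 28 days | 230 mg BID | 230 mg BID | agree |
| Recurrence on 460 mg BID, recovery in ≤ 28 days | 460 mg BID | 230 mg BID | conflict |
| Recurrence on 230 mg BID, recovery in ≤ 28 days | 230 mg BID | 230 mg BID | agree |
| No recovery by 28 days | stop | stop | agree |

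**How the two conflicts relate.** The recurrence conflict needs a patient still on 460 mg BID. Under the infection/fever row, the first episode already moves the patient to 230 mg BID. So the recurrence conflict arises mainly when the first episode was handled under the Grade 4 row with quick recovery. The other route is a dose raised again after reduction. The synopsis permits escalation of SM-88, but 5.6 mentions only interruptions and reductions and gives no rule for stepping up.

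**Does another sentence settle it?** Section 5.6 says that with multiple toxicities the worst one decides. Here one event meets two rows. Read by grade, the sentence selects the Grade 4 row. Febrile ANC < 500/mm³ with quick recovery then returns to 460 mg BID, while febrile ANC of 500–999/mm³, the milder event, is reduced to 230 mg BID. Read as ranking a complicated neutropenia worse, it selects the infection/fever row. The text does not choose.

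**Dose at stake.** 2 × 460 = 920 mg/day against 2 × 230 = 460 mg/day. Over a 28-day cycle this is 920 × 28 = 25,760 mg against 460 × 28 = 12,880 mg.

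**Exposure at stake** (section 1.4.3, pancreatic trial, Cycle 2; n = 8 at 460 mg BID, n = 10 at 230 mg BID, large SDs). AUC0-6 ratio: 24,805 / 16,808 = 1.48. Cmax ratio: 5,420 / 3,506 = 1.55.

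**Frequency.** Section 1.3 describes no Grade 4 neutropenia in 23 prostate patients (at most 460 mg/day) or 38 pancreatic patients (no Grade 4 or 5 treatment-related events). That is 0 of 61, with 19 of the 38 at this trial's dose. One-sided 95% upper limits are:

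- 1 − 0.05^(1/61) = 0.048, or 0.048 × 50 = 2.4 patients
- 1 − 0.05^(1/19) = 0.146, or 0.146 × 50 = 7.3 patients

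These bound all Grade 4 neutropenia. The overlap is the subset with infection or fever, and the main conflict needs quick recovery as well.

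**The case against.** The best defence is that the protocol can be read consistently. Section 5.6 says that for Grade 3 or 4 toxicity "dose modifications of SM-88 can be made as outlined in" Tables 4 and 5, and Table 4 answers toxicity at level 1 with 230 mg BID. The infection/fever row is also the more specific one for a febrile patient. Neither argument settles the matter. Table 4 is generic, and the Grade 4 row expressly restarts at the same dose, so using Table 4 as the tie-break would cancel that instruction for afebrile patients too. Letting the more specific row govern is sensible, but nothing says so.

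Two parts of the defence do stand. The recurrence conflict is largely a consequence of the first, so a reader who counts two independent conflicts overstates the problem. And the dose level is not the patient's only protection: supportive care includes antibiotics (3.5.2), blood counts are weekly during a hematologic hold (6.8.1), and the investigator may stop treatment at any time (4.3.12).

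A reader might also infer that the infection/fever row is unsafe because its restart test is ANC alone, whereas the rule for Grade 3 thrombocytopenia with bleeding requires platelet recovery "and bleeding stops within 28 days, resume drugs and decrease SM-88 to dose level -1". The documents do not support treating this as a defect to correct. Grade ≥ 3 infection already falls under the non-hematologic row. Table 5 requires no interruption for Grade 1–2 non-hematologic toxicity. Section 6.8.1 adds a general restart rule of Grade 1 or lower, or baseline if Grade 2 at entry. What remains is a matter of preference about low-grade infection or fever.

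**Conclusion.** Wrong as written, and minor in weight. For a first episode of ANC < 500/mm³ with infection or fever that recovers in at most 7 days, Table 5 prescribes both 230 and 460 mg BID. The difference is twofold in dose and about 1.5-fold in exposure, if the small pancreatic sample carries over.

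The event should be rare, and the number of affected patients may be zero. The limits of 2.4 and 7.3 patients in 50 are not forecasts of the overlap. They assume that undescribed events did not occur and that the earlier populations resemble this one. Most of the 61 patients were below the trial dose, and the pancreatic statement covers only treatment-related events.

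A reader might infer that site-to-site dose differences threaten the primary result. Nothing in the documents supports that: the ORR decision rule, its power and its error rates do not depend on these rows. The consequences are contradictory safety instructions and, at most, a few dose reductions counted inconsistently.

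**What to change.** Two wording changes in Table 5:

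- **(a)** Retitle the Grade 4 row: *Grade 4 neutropenia (ANC < 500/mm³) without documented infection or fever ≥ 38.5 °C*. Every case with infection or fever then falls under one row only, which by itself removes the contradiction.
- **(b)** In the recurrence bullet of the infection/fever row, replace the instruction to restart at the same dose with the Grade 4 row's own wording: "then decrease SM-88 to dose level -1 or resume drugs at same dose level if already at dose level -1". This is a backstop for any patient who reaches a febrile recurrence still on 460 mg BID.

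The restart condition and section 6.8.1 should be left alone. Making restart also depend on control of infection, with discretion after day 28, would clash with the maximum 28-day interruption in 6.8.1. A sentence giving Table 5 priority over 6.8.1 would alter the anemia and thrombocytopenia rules as well.

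The cost is an amendment to two rows, with no added visits or tests. The downside is that a rare patient restarts on 230 mg BID instead of 460 mg BID, with AUC0-6 lower by 1 − 16,808/24,805 = 0.32, or about 32%, on the pancreatic data.
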